The novel method of transcranial low-intensity focused ultrasound pulsation (LIFUP) as an attractive alternative that overcomes these limitations. LIFUP has the unique ability to non-invasively target deep brain nuclei, including specific thalamic areas, with remarkable precision of sonication focus²⁴. Despite the growing body of literature on LIFUP-induced behavioral modifications²⁵, its effect on conscious perception remains largely unexplored. Employing LIFUP to noninvasively modulate the activity of select brain regions has the potential to shed light on the intricate neural mechanisms of conscious perception in humans.

Research Objectives

The primary objective of this study is to investigate the causal role of thalamic areas in conscious perception using LIFUP. We hypothesize that stimulating different thalamic regions by LIFUP will result in distinct perceptual outcomes, potentially affecting subjective perception as quantified by criterion and detection sensitivity as described in detail under Data Analysis and Statistics.

To test these hypotheses, we have devised a three-fold approach:

1. We will conduct a near-threshold perceptual task to assess the perceptual outcomes under different conditions.

2. Utilizing transcranial LIFUP, we will selectively stimulate (both excite and inhibit) the anterior and posterior thalamic areas. These areas are chosen because they are known to be differentially enriched by matrix and core thalamic cells, respectively.
3. We will evaluate the quality of conscious contents using two orthogonal quantities derived from Signal Detection Theory: criterion (c) and sensitivity (d'). Criterion (c) represents a subject's tendency to report subjective recognition of a target stimulus, irrespective of its presence or absence. On the other hand, sensitivity (d') measures a subject's ability to differentiate between trials with a target present and trials with a target absent (**Figure 2**).

— Hit — Correct Rejection
— Miss — False Alarm

[figure not shown]

Figure 2. An overview of Signal Detection Theory

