We expect that exciting the matrix cell-rich areas of the thalamus, such as the ventral anterior section, will lead to a decrease in criterion (c), indicating a shift of the decision criterion towards a more liberal response bias. Conversely, exciting the core cell-rich areas of the thalamus, like the dorsal posterior section, will increase sensitivity (d'), resulting in improved differentiation ability in stimulus perception. Conversely, we also anticipate that inhibiting the ventral anterior thalamus will have the opposite effect on criterion (c), leading to a more conservative decision bias. Inhibiting the dorsal posterior thalamus will reduce sensitivity (d'), resulting in a decreased ability to differentiate between stimuli. By observing these effects, we aim to unravel the distinct causal roles of the anterior and posterior thalamus in conscious perception. This disentanglement will provide valuable insights into the mechanisms of specific thalamic regions in shaping perceptual processes.

Number of Subjects, Recruitment and Informed Consent

Our study will involve the enrollment of 60 participants, who will be randomly assigned to two groups, with each group consisting of 30 participants. The participants will be divided based on the type of transcranial LIFUP they will receive, either excitation or inhibition, targeting four specific thalamic areas. See experimental design details below. Healthy participants will be recruited by listing on UMClinicalStudies.org and by postings at area colleges and community groups in Ann Arbor. Interested volunteers will call the phone number of a designated recruiter for an initial phone screening. The initial phone screening will consist of questionnaires related to medical history, demographic information, handedness, inclusion and exclusion criteria. If interested, the participant will

complete the questionnaires, which will be reviewed by the study team. Once eligibility is confirmed by the study team, the one-time research study session will be scheduled. Participants may be screened for COVID-19 prior to entry into the hospital per hospital guidelines.

[figure not shown]

Figure 3. Randomized study group assignment. A total of 60 participants will be enrolled in the study and randomly assigned to two groups, each comprising 30 participants. The group assignment will be based on the type of transcranial LIFUP they will receive, either in the form of excitation or inhibition.

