Figure 5. Visual task design. During each 10-min session, participants will complete an image recognition task. Stimuli (faces, houses, and scrambled images) will be presented at the threshold of subjective recognition. Participants' task is to report the category ("F" or "H") of the image presented and their recognition experience ("Yes" or "No").

The stimulus set will include real and scrambled images, the latter will be created by phase-shuffling of a randomly chosen real image from each category to preserve category specific low-level image features^{41,42}. Because scrambled images serve as "catch trials" to determine the subjects' baseline tendency to give positive responses to a question about their recognition experience. The pre-stimulus interval will vary randomly from trial to trial between 2 and 4 seconds to prevent stimulus timing predictability. The stimuli will be presented in a randomized order to prevent category predictability.

Primary Outcome Measure

Perceptual criterion (c) and sensitivity (d') derived from the Signal Detection Theory (SDT) analysis. These measures will be assessed over a timeframe spanning from the baseline to 60 minutes after the LIFUP stimulation.

Data Analysis and Statistics

For each 10-min session, we will calculate sensitivity (d') and criterion (c) using subjective reports of recognition as "yes" or "no". (d') indicates the ability to discriminate between real and scrambled images. It is computed by subtracting the z-transformed False Alarms Rate (FAR) from the z-transformed Hit Rate (HR): $d' = Z(HR) - Z(FAR)$, where Z is an inverse normal cumulative distribution function. (c) reflects the tendency to make "yes" reports to indicate recognition, regardless of whether the stimulus is a real or a scrambled image, which is computed as: $c = -0.5 \times (Z(HR) + Z(FAR))$. We will also calculate percent of correct responses as an operational measure of two alternative-forced-choice sensitivity using subjective category reports, i.e., responses to the first question: "Face" or "House".

We will conduct a repeated-measures ANOVA, considering measurements taken during both the baseline and the four thalamic areas' stimulation sessions. This analysis will be

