performed at the group level to assess the effects of LIFUP on the perceptual measures. To determine statistical significance, we will apply a false discovery rate (FDR) correction and set the threshold at $\alpha < 0.05$. This approach will help us identify any significant differences between the baseline and the different thalamic area stimulations in terms of sensitivity (d') and criterion (c).

Anticipated Results and Interpretation

We expect to observe differential changes in the perceptual outcomes based on the LIFUP stimulation of different thalamic areas. We anticipate that stimulation of the ventral anterior thalamus will decrease criterion (c), indicating a shift of the decision criterion in the liberal direction. During exciting the dorsal posterior thalamus, we expect an increase in sensitivity (d'), reflecting a higher sensitivity in differentiating between stimuli. Conversely, when inhibiting the ventral anterior thalamus and the dorsal posterior thalamus, we expect the opposite effects on criterion (c) and sensitivity (d') compared to the outcomes seen during their respective excitations. The effects of stimulating the dorsal anterior thalamus and the ventral posterior thalamus are expected to lie between the effects of ventral anterior and dorsal posterior thalamic stimulation. These findings should provide valuable insights into the specific contributions of these thalamic regions in shaping conscious experiences.

Power Analysis

We considered a recent review article that summarized 25 LIFUP studies in humans. These studies had sample sizes ranging from 1 to 50, with a median value of 16. Since the neuromodulation effect is dependent on various factors, such as parameter settings and specific brain regions targeted, determining a prior effect size is challenging. However, we have planned a subject number of 30 per group, which exceeds the median sample size reported in the literature. With a larger sample size, we aim to enhance the statistical power, reliability and sensitivity of our findings, enabling us to draw robust conclusions about the neuromodulatory effects of LIFUP on conscious perception.

Biological Variables

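### No excitation-versus-inhibition comparison is pre-specified: the stated output is baseline-versus-area change, which is mixed with time on task

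*Combined protocol and SAP*

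**What the plan says.** The section on number of subjects enrols "60 participants, who will be randomly assigned to two groups, with each group consisting of 30 participants". The Figure 3 caption defines the groups: "The group assignment will be based on the type of transcranial LIFUP they will receive", that is, excitation or inhibition.

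Research Objectives makes signed predictions for each mode. Excitation of the ventral anterior area (VA) should lower c. Excitation of the dorsal posterior area (DP) should raise d'. For the other arm, "inhibiting the ventral anterior thalamus will have the opposite effect on criterion (c), leading to a more conservative decision bias", and d' should fall at DP. Anticipated Results and Interpretation repeats the expectation of opposite effects.

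Data Analysis and Statistics contains the only inferential plan: "We will conduct a repeated-measures ANOVA, considering measurements taken during both the baseline and the four thalamic" areas. The analysis is to be "performed at the group level to assess the effects of LIFUP on the perceptual measures", with an FDR correction at 0.05, in order to "identify any significant differences between the baseline and the different thalamic area stimulations" for d' and c. Neither the role of the randomised arm in the model nor the family of tests under the FDR rule is stated.

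Under Experimental Design, one 10-minute LIFUP-OFF baseline precedes four 10-minute LIFUP-ON sessions. The order of the four areas is counterbalanced. The position of the baseline is not, and no sham session is described.

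**The concern.** Randomisation is to mode of stimulation, and the prediction that the two modes act in opposite directions is a statement about the difference between the arms. The plan attaches no test to it.

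Every participant reaches each stimulated session after the baseline. A change from baseline is therefore the LIFUP effect plus whatever practice, fatigue or drift has built up. The stated contrasts cannot separate the two.

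Two contrasts in this design are better protected. In the between-arm difference in change, randomisation removes any shift common to both arms. In the comparison of one area with another inside an arm, counterbalancing balances session position. Neither is a stated output. If the between-arm comparison is added after results are known, it will be post hoc.

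**Working it through.** **What the text allows.** The phrase about group level has three possible readings.

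- Inference across participants: no arm term is implied.
- One ANOVA per arm. This is the likelier reading, because the document uses the word group for the randomised arm, and Power Analysis says "we have planned a subject number of 30 per group". The direction of change can then be examined in each arm, but the arms are not compared.
- One pooled ANOVA: the arm is ignored.

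None of these names a test of excitation against inhibition.

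**Inputs.** From the documents: n = 30 per arm, two outcomes, four areas, threshold 0.05 with FDR. Assumed, because the documents do not give them: effect sizes and time-on-task shifts (both in SD of change from baseline), two-sided tests, and the FDR family. Power Analysis rests on a literature median sample size and gives no effect size or power, so there is no planned figure to reproduce.

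**Single tests, unadjusted, non-central t.**

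Baseline versus one area in one arm: df = 29, critical t = 2.045, non-centrality = δ√30.

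- δ = 0.2: 0.2 × 5.477 = 1.095, rejection probability 19%.
- δ = 0.4: 0.4 × 5.477 = 2.191, rejection probability 56%.

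Between-arm difference in change: df = 58, critical t = 2.002, non-centrality = Δ√(30/2) = 3.873Δ.

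- +0.4/-0.4, Δ = 0.8: 3.098, power 86%.
- Inhibition half as strong, Δ = 0.6: 2.324, power 63%.
- Inhibition inert, Δ = 0.4: 1.549, power 33%.

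**False positives from time on task.** Suppose LIFUP does nothing and both arms shift by s. In one arm δ = s, so the baseline-versus-area test rejects 19% of the time at s = 0.2 and 56% at s = 0.4. Between arms Δ = s - s = 0, so the arm contrast rejects 5% of the time.

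**Comparing significance by arm is no substitute.** If both arms have the same true change of 0.4, exactly one is significant with probability 2 × 0.563 × 0.437 = 0.49.

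**What the remedy leaves uncured.** The baseline contrasts number 4 areas × 2 outcomes × 2 arms = 16. Two arm contrasts and four within-arm VA-versus-DP contrasts (2 outcomes × 2 arms) make 22. This family was simulated with 20,000 runs, Benjamini-Hochberg at 0.05, independent session noise, c and d' independent, and the shift equal in all four stimulated sessions.

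- With no LIFUP effect, the chance of at least one false baseline-versus-area finding inside the 22-test family is about 27% at a 0.2 SD shift and 89% at 0.4 SD. With the 16 tests alone it is about 32% and 93%.
- A rule that declares opposite effects from opposite within-arm signs plus the arm contrast can also mislead. With inhibition inert, an excitation effect of -0.8 SD on c at VA and a common shift of +0.4 SD, it fires falsely in about 18% to 23% of runs, depending on the effects assumed elsewhere.

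**The case against.** Four points on the other side have weight.

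- *The plan is silent; it does not contradict itself.* Two short sentences describe the ANOVA, and an arm term could be included without departing from them. This stands. A reader might infer that the plan rules out comparing the arms, or that it pools them so that opposite effects cancel. The text supports neither, and pooling is the less likely reading.
- *The objective concerns areas.* Research Objectives states: "The primary objective of this study is to investigate the causal role of thalamic areas in conscious perception using LIFUP". No objective asks whether excitation differs from inhibition as such, and signed predictions can be examined arm by arm. So the arm contrast should not be called a missing primary test. It matters because it is one of the protected routes to a causal statement.
- *The area comparison is partly there.* The five-level session factor already spans differences among areas. That is correct. But the factor also contains the baseline, so a significant overall effect could come from baseline against the rest, and no area-versus-area contrast is named as an output.
- *The confounding is a design feature.* Baseline first without sham would remain whatever model is fitted. This stands in full. A reader might infer that adding arm terms cures it, but the simulated figures above show that the within-arm tests stay exposed.

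The arm contrast also has limits. It removes only shifts common to both arms. It does not prove opposite signs, because one active and one inert mode would also produce a difference. In that case its power (33%) is below that of the single-arm test (56%).

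**Conclusion.** The point holds as an omission. No arm factor, arm-by-session term or excitation-versus-inhibition contrast is pre-specified. The stated output is confined to contrasts that are confounded with time on task, while the better-protected contrasts are not listed. This follows from the text and needs no assumed effect size.

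The size is illustrative only. Set test against test, a common shift of 0.2 or 0.4 SD gives 19% or 56% false rejection for a baseline-versus-area contrast and 5% for an arm contrast. If the modes truly act at +0.4 and -0.4, the arm contrast has 86% power against 56% in one arm, and that advantage reverses if one mode is inert. Effect size, shift size and sidedness are assumptions, and the single-test figures ignore the FDR correction.

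The documents do not support saying that the arms will never be compared, that the area objective is untested, or that rewording the analysis removes the time-on-task problem.

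**What to change.** Rewrite the analysis paragraph before results are seen.

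1. Specify a mixed ANOVA or linear mixed model with arm (between participants), session (within participants) and arm by session, and define what group level means.
2. Pre-specify the between-arm difference in change from baseline for c at VA and for d' at DP (2 tests).
3. Add the within-arm VA-versus-DP contrast for each outcome, for the area objective (4 tests).
4. Keep the 16 within-arm baseline-versus-area contrasts for direction only. State that they, and any claim of opposite effects that depends on their signs, remain confounded with time on task.
5. Define the FDR family, for example these 22 tests.
6. State that causal claims rest on the arm and area-versus-area contrasts, and that the arm contrast removes only shifts common to both arms.

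This needs no extra participants or procedures. The price is a larger FDR family and an arm contrast that is weaker than a single-arm test if one mode is inert. In simulations with 0.4 SD at the target area, half that at the two intermediate areas and none at the fourth, excitation-arm power for c at VA was 26/22/21% with 16 tests and 34/27/23% with 22 (inhibition symmetric, half-strength, inert). If all four areas respond equally, the larger family costs 2 to 4 points. Inside the 22-test family and under the graded profile, the arm contrast for c at VA had about 64%, 32% and 12% power. These figures depend on the assumed profile.

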Experimental Design. The experimental will consist of a 10-minute baseline period (LIFUP-OFF) followed by four 10-minute sessions of stimulating (LIFUP-ON) four thalamic areas. The order of thalamic area stimulation will be counterbalanced across participants and will include the ventral anterior (VA), dorsal anterior (DA), ventral posterior (VP), and dorsal posterior (DP) sections of the thalamus. The center coordinates of these thalamic regions will be derived from a previous study on thalamic parcellation ⁴⁰. Given that previous studies have not indicated any functional lateralization of the thalamic areas, we will target only the left hemisphere for the sake of convenience in this study.

Perceptual Task. The quality of conscious perception will be assessed by a well-established psychometric approach, the near-threshold perceptual task ^{41,42}. This task allows one to compare the neural activity evoked by identical weak stimuli that are sometimes perceived and sometimes remain subliminal (**Figure 5**). It thus rules out potential confounds of variability derived from the differences in physical property of the stimuli. All stimuli will be programmed using E-Prime (Psychology Software Tools, Pittsburgh, PA) and delivered via a laptop computer. Stimuli will be presented at the threshold of subjective recognition. An adaptive thresholding procedure will be conducted whereby image contrast will be titrated to reach a 50% subjective recognition rate for each subject. Stimuli will include two common visual object categories: faces and houses. Participants' task is to report the category ("F" or "H") of an image presented and their recognition experience ("Yes" or "No"). Specifically, they will be instructed to report the object category regardless of their recognition experience and, in cases of unrecognized images, to make a genuine guess (two-alternative choice discrimination). Then, they will be instructed to report whether they see an object, such that even if the object appears unclear or noisy, they should respond "yes", but if they see nothing or only low-level features, they should respond "no".

[figure not shown]

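### Area order is counterbalanced, but the stated ANOVA names no session-position term, so shared drift would enter the error and may lower power for area-versus-area comparisons

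*Combined protocol and SAP*

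**What the plan says.** Under Methods and Procedures, the Experimental Design paragraph sets out a "10-minute baseline period (LIFUP-OFF) followed by four 10-minute sessions of stimulating (LIFUP-ON) four thalamic areas". It adds: "The order of thalamic area stimulation will be counterbalanced across participants". It does not say how the orders are constructed (four sequences, all 24, or otherwise).

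The section on number of subjects has 60 participants "randomly assigned to two groups, with each group consisting of 30 participants", one group for excitation and one for inhibition.

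Data Analysis and Statistics gives the model in one sentence, which begins "We will conduct a repeated-measures ANOVA, considering measurements taken during both the baseline" and goes on to add the four area sessions. It is applied at the group level with FDR control at 0.05. No position, period or sequence term is named, and the counterbalanced order is not mentioned again.

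Two kinds of comparison are in play. The analysis section aims to "identify any significant differences between the baseline and the different thalamic area stimulations in terms of sensitivity (d') and criterion (c". The Research Objectives and the Anticipated Results are about differences between areas: "We expect to observe differential changes in the perceptual outcomes based on the LIFUP stimulation of different thalamic areas", with the dorsal anterior and ventral posterior areas expected to fall between the other two.

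**The concern.** Four areas given in turn to each participant, in varying order, form a four-period crossover. Counterbalancing spreads any effect of position (practice, fatigue, drowsiness) over the areas, so the area means are not systematically distorted. It does not remove that effect from the data. A participant who has an area fourth differs from one who has it first, and unless position is in the model this difference counts as unexplained within-subject variation. The error mean square rises and the tests between areas become harder to pass.

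Drift is plausible here, though not quantified. The same task is repeated over five 10-minute periods, contrast is titrated to each participant with no mention of doing so again between sessions, and the safety section lists sleepiness among common unrelated symptoms in earlier work. What is at stake is power for the area-versus-area hypotheses. The plan states no effect size, SD or power, so no known margin exists to absorb a loss.

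**Working it through.** **The plan's own figure.** There is none to reproduce. The Power Analysis section sets 30 per group because it exceeds a literature median of 16.

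**Inputs from the documents.** n = 30 per arm, a five-level within-subject factor (baseline and four areas), order counterbalanced over the four stimulation sessions, threshold 0.05.

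**Assumptions, not from the documents.** Session error SD 0.30 (variance 0.09), true difference between two areas 0.20 in d', linear drift with total change D from the first to the fourth stimulation session and the same in every participant, a two-sided 5% test of one contrast before FDR.

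**Step 1, error variance.** At the four positions the drift is 0, D/3, 2D/3 and D, with mean D/2. Squared deviations sum to 2(D/2)² + 2(D/6)² = 0.5556 D² per participant. Baseline is first for everyone, so its common drift goes into the baseline mean and not into the residual. The five-level ANOVA has 4 × 29 = 116 error degrees of freedom. The addition to the error mean square is 30 × 0.5556 D² / 116 = 0.144 D², and relative inflation is 0.144 D² / 0.09.

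**Step 2, power.** With balanced orders the contrast itself still varies with SD √(2 × 0.09/30) = 0.0775, because drift cancels from it. The reported standard error is 0.0775 × √(inflation factor). Approximate power is Φ((0.20 − 1.98 × reported SE) / 0.0775).

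| D | Error variance | Reported SE | Power, formula | Power, simulation |
|---|---|---|---|---|
| 0 | ×1.00 | 0.0775 | 73% | about 72% |
| 0.15 | ×1.04 | 0.079 | 71% | about 71% |
| 0.3 | ×1.14 | 0.083 | 68% | about 69% |
| 0.5 | ×1.40 | 0.092 | 59% | about 58% |
| 0.75 | ×1.90 | 0.107 | 44% | about 44% |

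The simulated column uses four sequences with 7 or 8 participants each, averaged over which sequences get the extra ones.

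**Step 3, with a position term.** Fitting area, position and participant to the four stimulation sessions leaves 3 × 29 − 3 = 84 error degrees of freedom. The standard error is 0.077 at every D and power is about 72%. With no drift, power is about 72% either way.

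**Step 4, direction of error.** In a separate simulation of the four stimulation sessions alone, n = 30, the overall area test without the term had a type I error of 2.6% at a drift of one residual SD, against a nominal 5%. The omission is conservative for area differences.

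**Step 5, balance.** 30/4 = 7.5 and 30/24 = 1.25, so neither four nor 24 sequences balance exactly within an arm, although 60/4 = 15 is exact overall. The resulting leak is small. If, over the two left-over participants, one area comes three positions later in total than another, the contrast shifts by 3 × (D/3)/30 = D/30, or 0.01 at D = 0.3 and 0.025 at D = 0.75.

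**Step 6, baseline contrasts.** An area is on average 2.5 sessions after baseline. If drift runs at D/3 per session from baseline on, the bias is 2.5 × D/3, or 0.25 at D = 0.3. A term for positions 1 to 4 leaves this in place.

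**The case against.** The strongest reply is that the comparison named in the analysis section is baseline against each area, and a position term does nothing for that. Baseline is always first, so its position cannot be separated from LIFUP-OFF. This stands and limits the point to area-versus-area comparisons. Those follow from the hypotheses, although no such contrast is written out.

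Second, the size rests on assumed drift. At D = 0.15 the loss is about one percentage point, and D = 0.5 and 0.75 are 1.7 and 2.5 residual SDs. A common drift is also the best case for a fixed position term. If individual drifts at D = 0.5 have an SD equal to their mean, power in the five-level model is about 38% without the term and 47% with it, a gain of 9 points against 72 − 58 = 14, and the 72% is not regained. This stands too.

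Third, the model is one sentence. A reader might infer that the plan rejects a position term, or throws away what counterbalancing buys. The text supports only that no such term is stated.

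A reader might also infer larger losses. Dividing the same sum of squares by three degrees of freedom per participant gives 0.185 D² / 0.09, or 19%, 51% and 116% at D = 0.3, 0.5 and 0.75. That belongs to an ANOVA of the four stimulation sessions alone. The plan describes five levels, for which the figures are 14%, 40% and 90%.

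**Conclusion.** The point holds as a gain in efficiency for area-versus-area comparisons and no further. As written, shared drift over the stimulation sessions would inflate the within-subject error and may reduce power. Under the assumptions above the loss runs from about 1 percentage point at a drift of half a residual SD to about 28 at 2.5 residual SDs (72 − 44). Whether it is negligible or material depends on a drift that the documents do not give.

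Two stronger conclusions are tempting and not supported. One is that the omission invalidates the area comparisons or creates false area differences; the test errs on the conservative side. The other is that the term would clean up the baseline comparisons. It would not, and analysing change from baseline does not solve that separate problem either. Because the term costs almost nothing when there is no drift, this is a free improvement.

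**What to change.** For the area-versus-area comparisons, specify a mixed model or crossover ANOVA of the four stimulation sessions with fixed effects for area and session position (1 to 4) and a participant effect.

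State the counterbalancing scheme and balance it within each arm as nearly as 30 allows. With four sequences, that is 7 or 8 participants per sequence. If two sequences have 8 in one arm, the other two should have 8 in the other arm, so that each sequence has 8 + 7 = 15 over all 60.

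Add a sentence saying that this does not remove drift from the baseline-versus-area contrasts, since baseline position is confounded with LIFUP-OFF, and that those contrasts need separate treatment.

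The cost is three degrees of freedom per model, a few lines of text and a revised allocation list. No extra participants or visits are needed.
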